3. INVESTIGATIONAL DEVICE & INTERVENTION

3.1 Intervention

3.1.1 Standard care (control) arm

As soon as the operation is finished and a wound dressing has been applied, the standard bandaging is applied. One layer of soft synthetic bandage, stretching from proximal tibia to distal femur covered by a further layer of crepe bandage prior to or after tourniquet deflation, with 50% overlap of each layer (cryotherapy can be applied over this if standard of care). The bandaging will be removed approximately 48 hours post-operatively whilst leaving the dressing in situ. The bandages can be removed sooner than 48 hours if the patients find them very uncomfortable, or in the event of any adverse events that would require their removal, or if a cryocuff is applied post-operatively.

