3.1.2 Andoflex TLC Calamine Lite compression bandaging (intervention) arm

As with standard bandaging, the Andoflex TLC Calamine Lite compression bandage will be applied over the routine surgical wound dressing. A foam inner bandage (Andoflex TLC Calamine Lite 2, Milliken Healthcare) is applied from the toe to the groin on the affected leg with minimal overlap. The second layer, which is the actual compression bandage (Andoflex TLC Calamine Lite 2, Milliken Healthcare) is applied at full stretch and with a 50% overlap of bandage to ensure adequate

compression in the application. The mode of action of this two layer compressive bandage kit is of particular practical use, since it is tolerable for patients overnight due to its low resting pressure. Furthermore, it produces high pressure compression with movement to stimulate the calf muscle pump. The bandage is applied from the toes upwards. The application of bandage from thigh to groin requires removal of the tourniquet first and so the leg is kept elevated until the bandaging is complete. There is a training video available on correct application of the bandages: https://www.youtube.com/watch?v=pal0pY_cTRc (Andoflex is known as Coflex in some other countries such as the USA).

The compression bandage has been shown to effect compression for up to a week. To balance compression and comfort, patients are asked to continue wearing the bandage for 5 consecutive days after surgery. The bandages can be removed sooner if the patients find them very uncomfortable (which will be classed as an adverse event) or in the event of any other adverse events that would require their removal – this will be recorded on the Case Report Form and in medical notes. If requested by the patient, they are allowed to return to a hospital clinic to have the Andoflex TLC Calamine Lite bandaging reapplied if for any reason the first set needed to be taken off. To maintain consistency, clinical healthcare professionals who apply a new Andoflex TLC Calamine Lite bandage need to sign a declaration that they have watched the training video and are comfortable complying with the instructions. Full product information on the Andoflex TLC Calamine 2-layer compression system can be found on the Andover Healthcare Inc website https://andoverhealthcare.com/product/coflex-tlc-calamine/

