5.5 Outcome measures

5.5.1 **Primary outcome measures**

To determine the level of operation-site related pain experienced at day 5 post-operation and to compare the average pain scores of patients in the control and Andoflex TLC Calamine Lite arm respectively, through administration of 10 cm visual descriptor scale (VDS) for pain.

The study is powered to detect the established minimal clinically important difference (MCID) of 1.5 cm on a 10 cm VDS pain.

5.5.2 **Secondary outcome measures**

All the outcome measures are summarised in Table 3.

Table 3. Overview of measurements

Weeks	-12 weeks to day of surgery	0 surgery	3 days ^{##}	5 days ^{##}	12 days [#]	6 weeks*	12 weeks *
Application bandage		Х					
straight after surgery							
VDS pain scale (at rest)	Χ		Χ	Χ	Χ	Χ	
VDS pain scale (walking)	Х		Χ	Χ	Χ	X	
McGill pain	Х		Χ	Χ	Χ	X	
questionnaire							
Limb range of motion	Х					X	
KOOS score	Х					X	Χ
Patient satisfaction					Χ	(X, if not	
questionnaire re						returned	
bandaging						yet at 12	
						days)	

^{*} Allowed to be up to 2 weeks early or late # Allowed to be up to 3 days early or late ## Allowed to be up to 1 day early or late

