8.3 Secondary outcome statistics

The average baseline demographics for participants in each group will be compared to ascertain that randomisation has indeed led to comparable distribution of participants:

Sex, age, height, weight, BMI, length of stay, type of anaesthetic for surgery and type of analgesics post-surgery.

To compare outcomes between the two groups (standard vs Andoflex TLC Calamine Lite bandaging), student t-test, Mann-Whitney U-test or Chi-squared test will be applied as applicable, depending on type and distribution of data .

Cox proportional hazards regression analysis will be conducted to investigate the role of bandaging and other covariates (as mentioned above) in post-surgery related pain and knee function.

The statistics apply to:

Up to 12 weeks prior to surgery, and 12 weeks post-surgery, knee function and quality of life measurements: Knee and Osteoarthritis Outcome Score (KOOS), and range of movement of the affected limb (goniometer)

Descriptive safety overview at 30 days and 12 weeks post-surgery:

- Readmitted to theatre and/or hospital
- Infection of wound site
- Diagnosed with pulmonary embolism or deep vein thrombosis
- All monitored remotely by review of patients' hospital notes.

Patient satisfaction survey at 12 days post-surgery – any difference in outcome will be determined with Mann-Whitney U-test

For all outcome measures and statistics, both whole cohort and surgery-specific stratification analysis will be conducted.

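### Wound infection, PE/DVT and readmission are taken from hospital notes with no patient, GP or other-hospital query, so events treated outside the Trust are likely to be undercounted in both arms

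*Protocol*

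**What the plan says.** Section 8.3 of the protocol sets out a "Descriptive safety overview at 30 days and 12 weeks post-surgery" covering readmission to theatre or hospital, wound-site infection, and PE or DVT. The source is fixed in the same list: "All monitored remotely by review of" the patients' hospital notes.

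Other parts of the protocol bear on how such events come to light:

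- **Table 3 (5.5.2)** schedules pain scales, the McGill questionnaire, range of motion, KOOS and a satisfaction questionnaire. It has no row for infection, clot or readmission.
- **Section 5.4** describes standard out-patient follow-up at 12 days and 12 weeks. It allows outcome data to be collected by phone, e-mail or mail.
- **Section 7.3** requires AE and SAE reports, with deadlines that run from the team becoming aware of the event.
- **Section 9** says GP practices are told that their patient is taking part. It does not say that event data are requested from them.
- **Section 3.1.2** says of intervention patients that "they are allowed to return to a hospital clinic to have the Andoflex TLC Calamine Lite bandaging reapplied if for any reason" the first set had to come off. Section 3.1.1 describes nothing equivalent for controls.
- **Section 10.2** says patients are not seen in clinic more often than in their normal care.

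**The concern.** Section 2 gives safety, alongside effectiveness, as an aim of the trial. The source of the safety outcomes is stated in the protocol itself, so it is not a detail held over to an analysis plan. A wound infection treated with antibiotics by a GP, or a readmission to a hospital outside the Trust, has no specified route into the count.

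The overview is labelled descriptive, but 8.3 places it in the list to which the between-arm statistics apply and asks for results in the whole cohort and by surgery type. The results also go to the manufacturer and to publication. With few events expected, low absolute rates could be read as reassurance when part of the shortfall comes from the method of looking.

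**Working it through.** The protocol states no event rate, capture rate or power for these outcomes, so there is no figure of its own to reproduce. The check has two parts.

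**1. Routes by which an event treated outside the Trust could enter the count**

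| Route | Where | Does it actively look for outside events? |
|---|---|---|
| Hospital-notes review | 8.3 | No. It finds what the notes already hold |
| AE/SAE forms | 7.3 | No. It depends on the team becoming aware, and no link to the 8.3 outcomes is stated |
| Out-patient follow-up at 12 days and 12 weeks | 5.4 | Possibly, if the patient mentions the event and it is written down; no question is specified |
| Research contacts at days 3, 5 and 12 and weeks 6 and 12 | Table 3 | No safety item is listed |
| GP practice | 9 | No. It is informed only |

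None of these routes actively seeks outside events. Wound infection is the outcome most exposed, because it can be managed in primary care. PE/DVT and return to theatre are more likely to be handled in hospital.

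**2. Size, as an illustration**

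Inputs: 74 per arm (section 1). The only event rate in the document is 2 DVTs in 47 osteotomy patients (section 2), and 2/47 = 4.3%. That is background literature on DVT, not a design assumption and not an infection rate, so I bracket it with assumed risks of 2% and 10%. Capture of 80% or 60% is also assumed.

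Detected events per arm = 74 × true risk × capture.

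| True risk | True events per arm | Found at 80% | Found at 60% |
|---|---|---|---|
| 2% | 74 × 0.02 = 1.48 | 1.18 | 0.89 |
| 4.3% | 74 × 2/47 = 3.15 | 2.52 | 1.89 |
| 10% | 74 × 0.10 = 7.40 | 5.92 | 4.44 |

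The loss runs from 1.48 − 1.18 = 0.30 to 7.40 − 4.44 = 2.96 events per arm. Within one surgery type (37 per arm) these figures halve. If capture is equal in the two arms, absolute rates are too low by 20% to 40% but the expected ratio between arms stays at 1.0.

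If capture differs, the apparent risk ratio under equal true risk is capture (intervention) ÷ capture (control):

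- control 80%, intervention 90%: 0.90/0.80 = 1.125
- control 60%, intervention 80%: 0.80/0.60 = 1.33
- control 80%, intervention 60%: 0.60/0.80 = 0.75

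At 4.3% risk, 60% against 80% means 1.89 against 2.52 events, a gap of 0.63 of an event. The protocol gives nothing with which to choose among these cases, including which arm would be favoured.

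**The case against.** **Other routes exist.** AE/SAE reporting covers both arms: hospitalisation meets the SAE definition, and infection or clot meets the AE definition. Out-patient visits generate notes in which an event treated elsewhere may be recorded. A case report form is mentioned but not shown, and it might hold a safety question. This stands as far as it goes: notes review is the only source named for these outcomes, but it is not the only way the team could learn of an event. It does not remove the point, because every visible route is passive. Section 5.4 is also unclear on day 12, which it names both as a standard out-patient visit and as a contact outside those dates.

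**The overview is descriptive and the trial is powered for day-5 pain.** This stands. With so few events, a between-arm difference would be hard to interpret even with perfect capture. The main loss is in the absolute rates.

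**A stronger reading is tempting:** that reapplication visits make detection higher in the intervention arm and would produce a spurious excess of events there. The documents do not support this.

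- The visits are optional, made at the patient's request, and arise only if the first bandage came off. They relate to a short wear period ("patients are asked to continue wearing the bandage for 5 consecutive days after surgery"), while the outcome windows run to 30 days and 12 weeks.
- The bandage goes over the wound dressing, and nothing says the dressing is lifted at reapplication.
- The direction could be the reverse. The intervention covers the leg from toe to groin for days. In the control arm the cover is shorter and comes off early: "The bandaging will be removed approximately 48 hours post-operatively whilst leaving the dressing in situ". Longer cover could delay recognition of redness or swelling.

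**Self-report has its own bias.** Patients can see which bandage they have. This stands, and the fix has to deal with it.

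**Conclusion.** The point holds as one of under-capture in both arms. As written, 8.3 has no specified means of finding wound infections treated by a GP or events treated at another hospital, and the AE route in 7.3 does not supply one. Under the assumed risks and capture above, the loss is a fraction of an event to about three events per arm. The true size is unknown, because the protocol gives no rate of care outside the Trust and the case report form cannot be seen.

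Unequal detection is a possibility that follows from offering return visits to one arm only. Neither its size nor its direction is shown, and no inflation factor should be attached to it.

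The primary outcome is untouched. The change is worth making because safety is a stated aim and the remedy is cheap.

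**What to change.** In 8.3 and Table 3, add one short question set, identical in both arms, to the existing day-12, week-6 and week-12 contacts. It asks whether, since the last contact, there has been:

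- a wound infection, or antibiotics for the wound from any prescriber
- a clot in the leg or lung
- a readmission or return to theatre at any hospital

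Each positive answer carries a date. Then:

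1. Use the dates to assign events to the 30-day and 12-week windows. Table 3 allows the week-6 and week-12 contacts to be two weeks early. A week-6 contact at week 4 (day 28) does not close the 30-day window, so late events must be placed by date from the week-12 contact. If that contact is made at week 10, the last two weeks rest on the notes alone, and this should be stated.
2. Keep the notes review. Confirm positive reports against available records and reconcile them with the AE forms.
3. Report confirmed and self-reported-only events separately by arm, with the source of detection.

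Sections 3.1.2 and 10.2 should also be reconciled on whether there are clinic visits beyond normal care.

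**Cost:** a few questions at contacts already planned and no new visits. Some reports will need checking, and checking with a GP goes beyond what section 9 now provides. Stated event rates may rise. Self-report comes from patients who know their allocation, which is why confirmed events should be shown apart from the rest.

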9. DATA HANDLING AND MONITORING

Data arising from this study is confidential. Identifiable information can only be accessed by delegated members of the study team. Anyone in the research team who does not have a substantive contract with Cumbria Partnership NHS Trusts or one of the recruiting NHS Trusts will need to apply for a letter of access via the NIHR research passport scheme, should they require access to identifiable study data.

Patient identifiable data will only be used within each respective Trust and by the core research team. All identifiable data is stored on password protected NHS computer systems. Anonymised data will be shared and stored using security-enabled systems such as password-protection and encryption of e-mails and files. The requirements of the Data Protection Act and NHS Code of Confidentiality will be followed at all times. All researchers will be fully trained in NHS Confidentiality and GCP. Participants' GP practices will be informed that they are taking part in the study.

All paper data will be held in secure locked environments in the office of the Research & Development department in the Cumberland Infirmary, Carlisle. Data released (e.g. by publication) will contain no information that could lead to the identification of an individual participant. Upon completion of the study the site files will be archived for a period of 15 years in line with local archiving policy and procedures. Direct access to data only will be granted to authorised representatives from the sponsor / host institution, grant funder and medical device provider (Milliken Healthcare) and the regulatory authorities to permit trial-related monitoring, audits and inspections.

This investigator-initiated trial will be monitored in terms of conduct of the study by the in-house research team, led by the Chief Investigator, who will convene on a monthly basis in person or via phone/e-mail. A formal trial steering committee will not be convened for this trial – however, when data is available for 50% of the sample an interim analysis will take place to assess if there are any points of concern to consider. The study can be audited by the in-house R&D department as part of their rolling audit programme of sponsored and hosted research studies. As part of the research grant agreement, anonymised study data will be shared with Milliken Healthcare for review and for potential publication purposes. No identifiable data, including on potential exemplar case photos, will be contained in any of this data.

10. GOVERANCE OF STUDY

10.1 Approvals

This study will be conducted in compliance with the protocol approved by the Health Research Authority, National Research Ethics Service, and local Trust R&D Approval, and according to Good Clinical Practice standards including the Declaration of Helsinki (1964, Amended Oct 2013). No deviation from the protocol will be implemented without the prior review and approval of the aforementioned review bodies, except where it may be necessary to eliminate an immediate hazard to a research subject. In such case, the deviation will be reported according to policies and procedures

10.2 **Sponsor & Indemnity**

North Cumbria Integrated Care NHS Foundation Trust is the sponsor of this study and therefore NHS indemnity applies for design, conduct and management of the study. Milliken has provided a grant for this study by means of provision of the Andoflex TLC Calamine Lite bandaging material worth £1,000.

Patients will not be given financial incentives for taking part in the study. Travel expenses are not offered in this study since patients are not seen in clinic more frequently than they would normally attend as part of their normal care pathway.

11. PUBLICATION AND DATA-SHARING POLICY

The study will be registered on ISRCTN or Clinical Trials Gov website, in line with CONSORT guidelines on good practice in clinical research.

The results of this study are planned to be disseminated through:

- Peer-reviewed manuscript in scientific journal
- Internal report to the funder of the trial, Milliken

As stated in the PIL and ICF, anonymised study data will be shared with Milliken as part of the research grant agreement.

A summary of the main findings can be supplied to participants on request and this will be stated in the informed consent form.

APPENDIX 1. TOOLS AND ASSESSMENTS

[figure not shown]
This appendix contains:

- Visual Descriptor Pain scale
- Short-form McGill pain questionnaire

The KOOS score and Bandage Patient Satisfaction Questionnaire are enclosed separately to this protocol.

Visual Descriptor Pain score

[figure not shown]
How painful has your leg, the one has been operated on, been in the last day when resting:

Please put a vertical line on the numbered bar above. We kindly ask you consider the affected knee when you answer this question.

Visual Descriptor Pain score

How painful has your leg, the one has been operated on, been in the last day when walking:

Please put a vertical line on the numbered bar above. We kindly ask you consider the affected knee when you answer this question.

Short-form McGill pain questionnaire

[figure not shown]
How painful has your leg, the one has been operated on, been generally in the last day

PATIENT'S NAME:			DATE:	
	NONE	MILD	MODERATE	SEVERE
THROBBING	0)	1)	2)	3)
SHOOTING	0)	1)	2)	3)
STABBING	0)	1)	2)	3)
SHARP	0)	1)	2)	3)
CRAMPING	0)	1)	2)	3)
GNAWING	0)	1)	2)	3)
HOT/BURNING	0)	1)	2)	3)
ACHING	0)	1)	2)	3)
HEAVY	0)	1)	2)	3)
TENDER	0)	1)	2)	3)
SPLITTING	0)	1)	2)	3)
TIRING/EXHAUSTING	0)	1)	2)	3)
SICKENING	0)	1)	2)	3)
FEARFUL	0)	1)	2)	3)
PUNISHING/CRUEL	0)	1)	2)	3)
VAS N				WORST POSSIBLE PAIN
PPI				100
0 NO PAIN 1 MILD 2 DISCOMFORTING 3 DISTRESSING 4 HORRIBLE 5 EXCRUCIATING	\equiv			© R. Melzack 1984

[figure not shown]
The short-form McGill Pain Questionnaire (SF-MPQ). Descriptors 1–11 represent the sensory dimension of pain experience and 12-15 represent the affective dimension. Each descriptor is ranked on an intensity scale of 0 = none, 1 = mild, 2 = moderate, 3 = severe. The Present Pain Intensity (PPI) of the standard long-form McGill Pain Questionnaire (LF-MPQ) and the visual analogue scale (VAS) are also included to provide overall intensity scores.

The McGill Pain Questionnaire: Major properties and scoring methods. Melzack, 1987

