	 37 Patients to receive non-compression bandaging 37 Patient to receive Andoflex TLC Calamine Lite dual-layer compression bandaging 					
	Therefore total is:					
	- 74 knee replacement cases					
	- 74 osteotomy cases					

	Overall trial sample size: 148				
Primary objective	To determine the level of operation-site related pain experienced at day 5 post-operation and to compare the average pain scores of patients in the control and Andoflex TLC Calamine Lite arm respectively, through administration of 10 cm visual descriptor scale (VDS) for 'at rest' pain.				
Secondary objectives	Post-operative patient-reported outcome measures:				
	Prior to surgery and 3, 5, 12 days, and 6 weeks post-surgery - Pain perception, using VDS pain (at rest and walking) and short form McGill pain questionnaire				
	Prior to surgery as baseline, and 6 and 12 weeks post-surgery, knee function and quality of life measurements				
	 Knee and Osteoarthritis Outcome Score (KOOS) Range of motion of the affected limb 				
	Descriptive safety overview at 30 days and 12 weeks post- surgery:				
	 Readmitted to theatre and/or hospital Infection of wound site Diagnosed with pulmonary embolism or deep vein 				
	thrombosis. Patient satisfaction survey at 12 days post-surgery				
Sponsor	North Cumbria Integrated Care NHS Foundation Trust				
Manufacturer & research grant provider	Milliken Healthcare Inc				
Chief Investigator	[name], consultant Orthopaedic Surgeon. North Cumbria Integrated Care NHS Foundation Trust. Phone numbers: [contact] (Secretary); [contact] (office), Email: [contact]				
Co-investigators	[name], consultant Orthopaedic Surgeon. North Cumbria Integrated Care NHS Foundation Trust, [contact]				
	[name], consultant Orthopaedic Surgeon. North Cumbria Integrated Care NHS Foundation Trust, [contact]				

	[name] PhD, Science & Innovation Manager, [contact] or [name]; [contact] North Cumbria Integrated Care NHS Foundation Trust R&D Department, [name] [name], Orthopaedic Specialist Practitioner, North Cumbria University Hospitals NHS Trust, [contact] [name], Advanced Nurse Practitioner, North Cumbria University Hospitals NHS Trust, [contact]
Organisation where research will take place	North Cumbria Integrated Care NHS Foundation Trust Orthopaedics Department [name]

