6.2.2 Exclusion criteria

- Under the age of 18 years
- Unable to fully understand the consent process and provide informed consent due to either language barriers or mental capacity
- Revision of previous knee replacement or osteotomy on the index leg.
- Limited life expectancy, i.e. undergoing palliative care
- Any condition that is associated with excessive bleeding, coagulation abnormalities or any other significant haematological condition (e.g. Factor V Leiden, haemophilia).
- Cardiovascular or vascular condition that in the opinion of the treating surgeon contraindicates the use of compression bandaging, including moderate to severe peripheral arterial disease, venous leg ulcer, high dose anti-coagulant medication
- Any skin or other condition that contraindicates the use of compression bandaging, including diabetic foot ulcer or peripheral neuropathy.
- Patients who are participating in another interventional research study involving an investigational product related to the knee procedure and its aftercare.
- The patient has concurrent (medical) conditions that in the opinion of the investigator may compromise patient safety or study objectives.
- Patient has practical or mobility issues which will prevent them from removing the bandage themselves

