8.2 Primary outcome statistics

To determine the level of operation-site related pain experienced at day 5 post-operation and to compare the average pain scores of patients in the control and Andoflex TLC Calamine Lite arm respectively, through administration of 10 cm visual descriptor scale (VDS) for pain.

Confidential – This document and the information contained herein may not be reproduced, used or disclosed without written permission from North Cumbria Integrated Care NHS Foundation Trust Page | 18

The study is powered to detect the established minimal clinically important difference (MCID) of 1.5 cm on a 10 cm VDS pain.

The average difference between time points will be calculated per group, 5 days post-surgery weeks being the primary endpoint. Three days, 12 days and 6 weeks post-surgery will also be analysed. To compare the groups, the Mann-Whitney U-test will be applied.

To avoid relying on one outcome measure related to pain, at 3, 5, 12 days, and 6 weeks post-surgery pain perception will also be measured using the short form McGill pain questionnaire. Again, to compare groups the Mann-Whitney U-test will be applied.

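### The pain forms scheduled before surgery ask about a leg that has already been operated on, so patients with earlier surgery on the other knee may score the wrong leg at baseline (minor).

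*Protocol*

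**What the plan says.** **Timing.** The secondary objectives in the research protocol summary place pain perception (VDS at rest and walking, and McGill) at these points: "Prior to surgery and 3, 5, 12 days, and 6 weeks post-surgery". Table 3 in section 5.5.2 marks all three instruments in the column that ends on the day of surgery. Section 5.4 says baseline may be collected on that day before the operation. It also allows any outcome measure to be completed by phone, e-mail or mail.

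**Wording.** Appendix 1 supplies one version of each form:
- VDS at rest: "How painful has your leg, the one has been operated on, been in the last day when resting"
- VDS walking: "How painful has your leg, the one has been operated on, been in the last day when walking"
- McGill: "How painful has your leg, the one has been operated on, been generally in the last day"

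Both VDS forms add: "We kindly ask you consider the affected knee when you answer this question". The readable McGill text has no such line. Appendix 1 says the KOOS and the satisfaction questionnaire are enclosed separately, but mentions no separate pre-operative pain form.

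**Eligibility.** The only exclusion in section 6.2.2 that concerns earlier knee surgery is "Revision of previous knee replacement or osteotomy on the index leg". Section 6.2.1 admits double knee replacement and designates one leg as the index leg.

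**Use of the data.** Section 8.2 states: "The average difference between time points will be calculated per group". It names day 5 as the primary endpoint and compares the arms with a Mann-Whitney test.

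**The concern.** At baseline the study operation has not taken place, so the question on all three forms has no literal referent in the trial. Most patients will work out which leg is meant. A patient who has already had the other knee replaced or realigned is different: the only leg that literally matches the question is the wrong one. A form completed at home gives staff no opportunity to notice.

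What is at stake is the quality of the baseline pain values and of any change computed from them. The error could not be repaired later, because the readable forms do not record which side was scored.

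**Working it through.** The point rests mainly on setting the sections side by side. The protocol states no figure for it.

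1. **Are the forms used before surgery?** Yes: the summary, Table 3 and section 5.4 agree.
2. **Does the wording fit that use?** No. All three questions presuppose a completed operation, and no other version is shown or mentioned.
3. **Can an eligible patient have an operated leg that is not the index leg?** Yes. Section 6.2.2 restricts the earlier-surgery exclusion to the index leg.
4. **Does anything on the form resolve the ambiguity?** Partly. The VDS line directs the patient to the affected knee, but it shares the form with a question that may point to the other leg. None of the readable forms uses the term index leg.
5. **Does it reach the primary comparison?** Not through the baseline wording. The endpoint is at-rest VDS pain at day 5, after the operation. Baseline enters only if the difference between time points in section 8.2 means change from baseline. That section does not name the reference point, and the time points it lists are all post-operative.
6. **Would the error differ by arm?** It should not. Baseline precedes application of the bandage, so misreading is expected to be balanced.

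**Illustration only.** From section 6.1: SD 2 cm, target difference 1.5 cm, 62 evaluable patients per surgery type. That 62 reproduces as 31 per arm for a two-sided Mann-Whitney test (relative efficiency 3/π, effect size 0.75, power 0.81).

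Assumed, not in the documents: index-knee baseline mean 5 cm, other knee 2 cm, SD 2 cm for both; other-knee score uncorrelated with day-5 pain; correlation ρ of index-knee baseline with day-5 pain 0.3 to 0.7; share q scoring the other leg 5% to 30%.

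- Shift in baseline mean, expected alike in both arms: 3q = 0.15 to 0.9 cm too low.
- Variance of observed baseline: 4 + 9q(1 − q).
- Covariance with day 5: 4ρ(1 − q).
- SD of change: √[4 + 4 + 9q(1 − q) − 8ρ(1 − q)].

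For ρ = 0.5:
- q = 0: √(8 − 4) = 2.00
- q = 0.05: √(8 + 0.4275 − 3.8) = √4.6275 = 2.15
- q = 0.30: √(8 + 1.89 − 2.8) = √7.09 = 2.66

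Power of a change-score comparison with 31 per arm, from Φ(1.5 / (SD·√(2/31)) − 1.96):

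| ρ | q = 0 | q = 0.05 | q = 0.30 |
|---|---|---|---|
| 0.3 | 0.70 | 0.66 | 0.54 |
| 0.5 | 0.84 | 0.78 | 0.60 |
| 0.7 | 0.97 | 0.92 | 0.68 |

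A comparison of day-5 scores alone does not involve q and is unchanged.

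**The case against.** The strongest reply is that this is a slip of wording with little consequence. Elsewhere the protocol uses affected for the study limb, as in the range-of-motion measurement, so the VDS instruction points a patient awaiting surgery to the right knee. The missing McGill line is weak evidence, because figures around that form are not shown. All of this stands, and it is why the risk is described as possible and confined to patients with earlier surgery on the other leg.

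Three stronger readings are tempting, and the documents do not support them.

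- **That baseline does not measure index-knee pain in general.** For a patient with no earlier leg surgery, only the knee awaiting surgery can sensibly be meant.
- **That power from baseline adjustment is lost.** No such adjustment is planned. Section 8.2 specifies an unadjusted Mann-Whitney test, and the covariates listed in section 8.3 do not include baseline pain.
- **That the treatment effect is distorted, or that one patient's scoring error can be set against the 1.5 cm target.** That target is a difference between arm means. A mis-scored baseline is an individual error expected alike in both arms, so it adds noise and does not bias the difference.

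The reply does not remove the mismatch itself. The forms are scheduled for a visit their question does not fit, and the VDS line leaves two cues that may name different legs.

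**Conclusion.** The point holds as a minor defect of the instrument. The wording is wrong for one scheduled use, and some eligible patients may score the other leg because of it. The result is noise in baseline pain and in change from baseline, if section 8.2 intends such a change. The between-arm comparison at day 5 is not biased.

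The size cannot be derived from the documents, which give neither the share of patients with earlier surgery on the other knee nor how many would follow the wrong cue. The figures above are upper-end illustrations: they take every mis-scored baseline as unrelated to day-5 pain and assume a 3 cm gap between knees. They also matter only if change from baseline is analysed. The conclusion that the error is balanced rests on baseline being taken before the bandage is applied.

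**What to change.** Add to Appendix 1 a pre-operative version of the VDS at rest, the VDS walking and the McGill that asks about the knee that is going to be operated on in this study, with left or right pre-filled by staff. Keep the present question for post-operative visits and pre-fill the index side there too. This also settles which leg is meant for double-replacement patients, for whom the current question stays ambiguous after surgery, including at day 5.

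The cost is one extra version of three short forms and a minor amendment. No visits, staff or patients are added, and the sample size does not change.
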